The dietary fiber has a role in the Very Important gastrointestinal tract, esta happens With any non-digestible carbohydrate (CH) That gets to the color, ferments intestinal bacteria Where it partially or completely, for short chain fatty acids (SCFA) and gases. Dietary fibers can be associated gastrointestinal symptoms With, mainly flatulence, abdominal distention and pain, as well as meteorism, due to the anaerobic bacteria in the fermentation of fiber colon⁶.

Many types of fiber Have Been Used, Plantago Psyllium being The One with more scientific evidence backing it up, starting at dose of 10g per day, at Least for 4 Weeks with an average response of 57%. Plantago psyllium is a long chain Considered moderately fermentable CH; it is a type of mucilage That Provides viscosity to stool through formation of gels I related to a peristaltic action in the intestine and Causing Increase in the intestinal motility. It is one of the agents of fecal matter forming Most Used for constipation control⁷⁻⁸. Among the contraindications for ITS use are: intestinal obstruction and sub-occlusion, abdominal pain, nausea, hypersensitivity, flatulence, abdominal distension and severe meteorism⁹. ACCORDING to the American Gastroenterological Association Medical Position Statement on Constipation (AGA) They recommend Plantago Psyllium With a supplementation of 15g / day in Patients With Functional constipation¹⁰.

The genre, Agave Tequilana Webber var. Blue stands out as an agronomically and economically crop in Mexico Important Which has relevance in the national and the international market, Besides its usefulness in the sugar and soluble dietary fibers, for ITS prebiotic fructans and Its beneficial effect ability in health. About 60-85% of the carbohydrates in agave are fructans and the type of link β (2-1) presents it causes the salivary, gastric and enteric enzymes not to be hydrolyzed by humans, Which causes them to arrive intact to the intestine and can be subject to fermentation by the colon microbiota, especially bifidobacterial by. It Has Been Reported That Can Regulate the intake ITS lipid metabolism through the synthesis of triglycerides, and thanks to it soluble fiber percentage, beneficial effect It provides on the gastrointestinal physiology,

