The gastrointestinal symptoms are produced in a fast way and taken as They are side effects or intolerance. On the other hand, reference to the tolerance Makes development of "no response" Referring to SpecificallyLDCs, The tolerance Refers to the absence of gastrointestinal symptoms After their intake.

Tolerance is different in every subject and it is influenced by the different factors presented down (Fig. 1), furthermore, influenced by the They are amount ofLDC concentration, the amount of food consumed, the frequency of the consumption, consumption of other food (that Increase tolerance), and the presence of water (Decreases tolerance) 36.39.

Regular LDCintake can improve increase the intestinal microbiota ability to ferment carbohydrates's (bacterial adaptation), in Addition to decreasing diarrhea as symptoms Such (clinical adaptation). Additionally, the intake of small doses of These fructans Throughout the day can decrease the presence of symptoms, and With a regular intake, the dose can be Increased without Increasing the symtoms36,37,39.

toxicologic elimination

In order to determine if inulin / oligofructose and FOS are safe for ingestion in high Concentrations, toxicology safety studies Have Been Carried out in mice and rats expose to a diet With FOS (0, 3, 6 and 9 g / kg) (average DP 3.5) for 10 weeks. The results Showed That FOS do not Affect state of health or rats and mice Makes weight gain FOS When They are administered doses of 9g / kg. In another study Carried to evaluate- out in Wistar rats Subacute Toxicity (SPF) Where the dose 1.5, 3 and 4.5 FOS / kg dose was tested, for 6 weeks. On the 2nd, 4th and 6th week blood samples Were taken from the animals and after That They Were sacrificed in order to

Obtain the liver, kidney, brain, cerebellum, heart, lungs, spleen and the pituitary gland. The results revealed no abnormalities That Were Examined found in the organs, there is no concluding That toxicity related with the treatment in any of the groups Treated With FOS Until a 4.5g / kg dose for 6 weeks.

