
Bruhwyler, J, et al / 2009
 
Sample size = 84 healthy volunteers Age (18-45 years) BMI: 25.1 kg / m² Total fiber intake 12 g
	
Randomized, double-blind, placebo-controlled, crossover clinical trial
 
 1. Fibrulose F97 (5 and 20 g / day) 2. Instant Fibruline (5, 10 and 20 g / day) 3. Fibruline XL (10 g / day) 
vs. Placebo
 
Five two-week periods: placebo treatment 1 wash With placebo, treatment 2 placebo withdrawal
	
Digestive symptoms:
 
All three products Tended to Increase digestive symptoms (flatulence, Borborygmus, distention, abdominal pain, abdominal cramps, nausea, evacuation frequency and stool consistency) Regardless of the dose. Changes Were mild (maximum, +19 mm 800 mm on the scale) and significant ($p < 0.001$) for Instant Fibruline at 20 g / day. Significant Difference between Fibruline Instant and Fibrulose F97 ($P = 0.011$), with 20 g / day Presence of dose-effect relationship: both for Fibrulose F97 ($P > 0.05$) as for Fibruline Instant ($P = 0.042$). The rest of the treatments Were not significant.

Bonnema, A. et al 2010
 
Sample size = 26 13 men, BMI: 24 ± 2 13 women, BMI: 23 ± 3 Age: 18 to 60 years.
	
Double-blind, placebo-controlled, crossover study
 
Treatment groups every week 10
 
 I. 5g oligofructose II. 10g oligofructose III. 3. 5g inulin IV: 10g inulin V. Placebo: 5g maltodextrin 10g maltodextrin 
Intervention: 1 bagel (120 g), 28g cream cheese 296 mL orange juice. + 1 of the treatments in the orange juice
	
GI tolerance through assessment questionnaires: 0, 2, 4, 24 and 48 hours
 
Gastrointestinal symptoms: Both inulin fibers tend to lightly Increase the symptoms.
 
Most frequent symptoms: Flatulence followed by distention. 10g dose oligofructose Increase the GI symptoms vs Control Native inulin dose up to 10g / day and up to 5g / day of oligofructose Were well tolerated by the subjects. The symptoms Were not consistent Among the subjects; MOST of them did not Have When tolerance problems to inulin or oligofructose adding Their breakfast.

Telephone evaluation During five visits during breakfast	in each visit	
--	---------------	--

1. Evidence of studies With Agave

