What is more, preliminary studies the use of proven Have Agave fructans as prebiotic effect in in vitro models, as well as healthy subjects. . Gomez et al, (2010), through and in vitro study, Observed the properties and the potential prebiotic activity of Agave fructans, Compared with 5 types of soluble fiber of commercial brands: Synergy, FOS-Raftilose, Predilife, Actilight, Inulin HP Cellulose and to control. The prebiotic and the short chain fatty acid production in Said Were EVALUATED study, through the comparison of discontinuous anaerobic cultures and Inoculated With human feces. The results Obtained Showed a significant Increase of bifidobacteria and lactobacillys ($p = <0.05$) in the fructan Compared With cellulose substrate.

Holscher et al., (2014), Through a randomized, double-blind, controlled, crossover clinical trial, EVALUATED the gastrointestinal tolerance in healthy subjects With an Agave inulin Where significant Increase of the symptoms: such as bloating, flatulence and borborygmus in subjects Who Took 5 and 7.5g of Agave inulin Compared to the controls (0g), with significant Differences in distention and Borborygmus ($p <0.05$) as well as an Increase in the subject's number of evacuations Who Took the 7.5g dose ($p <0.05$), however, the presence of symptoms was well tolerated by the healthy subjects. Conversely, was an Increase in the production of Observed Compared to the H₂ statistically significant difference in the groups That Took Agave inulin (5 and 7.5g) vs controls ($p <0.001$) 38.

Holscher et al.(2015) Carried out a crossover study in three healthy subjects 29 periods Where Were Given 5 and 7.5g of agave inulin for 21 days with 7 days of washing Between periods; Their subjects recorded the daily dietary intake and fecal samples Which Were Collected underwent fermentation 16s Illumina sequencing and analysis. The results Obtained Showed That the subjects ingested 7.5g of WHO agave inulin did not report adverse effects and the subjects ingested WHO 5 and 7.5g of agave inulin the number of Significantly Increased faecal Bifidobacteria (basal = 1.7 vs 4.9 Final $p <0.01$). Compared to the controls did not ingest agave That inulin50.

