The initial treatment of Patients with Functional constipation is based on fiber. There are multiple fiber products in the market, which are Promoted as a supplement for constipation without any scientific evidence to support ITS use. Furthermore, the tolerability of These compounds limits long-term Their use in esta patient population. Scientific evidence is required to support the effectiveness in the use of These fiber supplements in Patients With functional constipation.

6. Justification

There are multiple fibers are in the market That Promoted as a beneficial supplement for Patients With constipation, DESPITE esta, there is not enough scientific evidence derived from randomized and controlled studies to support ITS use. THEREFORE, it is Necessary to Provide evidence to support the use of blue agave fructans Tequilana Weber in Patients With functional constipation.

7A. hypothesis

Defined as a verifiable statement About the relationship Between a variable-dependent and an independent variable. (Remember That the concepts of "null hypothesis", "alternate hypothesis" are related to the statistical analysis So They Should not be included in this item)

General Hypothesis:

Plantago Psyllium When Compared With, the blue agave fructans Weber Tequilana have a like effect or are more effective in Improving functional constipation in adult patients.

Objectives

PRIMARY

1. To Evaluate the efficacy of the blue agave fructans Tequilana Weber in Patients With functional constipation.

SECONDARY

1. To compare the efficacy and tolerability of 5 and 10g doses of blue agave fructans Tequilana Weber in Patients With functional constipation.
2. To Evaluate the impact of the consumption of blue agave fructans Tequilana Weber on the quality of life of the subjects WHO ingest it by Applying the quality of life questionnaire SF-36.
3. To determine the impact of the blue agave fructans of Weber Tequilana intake in the fasting glucose, glycosylated hemoglobin A1c and the lipid profile (metabolic profile) of the subjects WHO ingest it.
4. To Evaluate the presence of short chain fatty acids (butyrate) before vs after the treatment with blue agave fructans Tequilana Weber.
5. To determine the impact of the ingestion of blue agave fructans Tequilana Weber in the microbiota before vs after ingestion.
6. Evaluate to the tolerance to the ingestion of blue agave fructans Weber Tequilana through the use of breath test.

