effects on intestinal transit Have Been observed from the first week of intake, in fact this is one of the Reasons to focus the study on functional constipation and intestinal transit.

Breath test:

A breath test will be Carried out in order to measure hydrogen and methane Concentrations previousle Exhaled In Patients randomized in visits 1 and 5.

In order to carry out the breath test gas chromatography equipment will be used, brand Quintron Breath Tracker.

For That, The Patients will be Asked:

- Not to take antibiotics prior weeks At least to the test.
- Stop the intake of food rich in fibers and starches 24 h before the test.
- Not to take alcohol, or smoke
- Have a minimum of 8 hours fasting
- Perform oral hygiene before starting the test and during the performance of measurements.

This test lasts 3 hours, during which the patient can not leave the laboratory facilities motility, can not speak too much or sleep. Exhaled air samples are taken every 15 minutes during this period.

SmartPill®:

[figure not shown]
SmartPill® test will be conducted on visits 2 and 4.

colonoscopy:

Colonoscopy study is a tool which will be subject to scrutiny patients ≥ 55 years with newly diagnosed constipation or those where changes in bowel habits observed in this age group. This fundamental objective, rule out potentially serious diseases and not to delay the diagnosis of these during the research study. one colonoscopic study all patients who have constipation and any of the following characteristics will be used:

1. Diagnosis of constipation less than 1 year
2. Subjects ≥ 55 years who do not have colonoscopic evaluation in the last 3 years prior to study entry
3. Chronic but with alarm data (: Unexplained weight loss, recent transrectal bleeding < 6 months, recent changes in the defecation pattern example) Constipation

Study Flow Chart

Patients include:

Studies with fiber supplements (Psyllium, Plums⁸) Have included 25 to 30 patients per group to find differences between groups.

In total it is planned to include 60 patients randomized as follows: 15 patients receive fructans blue agave Tequilana Weber dose of 5 g, 15 patients received the dose of 10 g, 15 patients received the dose of 5g of agave fructans blue Tequilana Weber + 10 g excipient and 15 patients received 15 g plantago psyllium.

9. Methodology Selection Criteria

a) Inclusion criteria (consider not participating in other research and contraception if necessary)

- Patients over 18 years old.

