Discomforts generated by the study:

Discomfort from the study are related to the puncture for blood collection (3). It is anticipated that the fiber, when containing fructans, generate a fermentation process with flatulence and bloating. However, reports of studies using the fiber, have shown that this effect is transient lasting 2 weeks.

Risks:

Regulation of the General Law of Health in Research for Health, said that obtaining biological samples represents a minimal risk in the investigation. The risks of blood sampling are: possibility of slight bleeding or bruising at the puncture site, dizziness or fainting and rarely arterial puncture may occur. Personnel draw the blood sample is trained for this, which will minimize the risks of complications.

If there are complications will be referred directly to your treating physician. It is anticipated in the informed consent we do not have resources in case complications arise.

Benefits:

Administration fiber, it has shown to be healthy and beneficial for the treatment of functional constipation. Such supplementation, is the first line treatment of functional constipation. Patients entering this study will benefit from fiber start treatment within the diagnostic and therapeutic approach constipation.

Moreover, thanks to the participation of volunteers, your community can benefit significantly by finding new ways to address this medical complication.

Rescue measures:

If the patient has no spontaneous evacuation after 72h will prompt the patient to contact the research team, for instructions such as laxatives previously prescribed by your physician. If distended or flatulence, using anti detergents (simethicone) that is effective to treat this condition is allowed. For present colic, it can be used a conventional antispasmodic. each of the side effects will be recorded as well as the need for therapies rescues specified above.

13. Schedule of activities

The letter updating the research project is attached. (Annex 1)

Activities	2018												2019												2020											
	J	F	M	A	M	J	J	A	S	O	N	D	J	F	M	A	M	J	J	A	S	O	N	D	J	F	M	A	M	J	J	A	S	O	N	D
Moith																																				
Research topic selection	■																																			
Search and review of the biography	■	■	■	■	■	■	■	■	■	■	■	■	■	■	■	■	■	■	■	■	■	■	■													
Protocol writing	■	■																																		
Review of the protocol by the research group			■	■																																

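### Secondary objective 6 judges tolerance by a breath test, which measures fermentation; tolerability should be judged from the symptom records the trial already collects

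*Combined protocol and SAP*

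**What the plan says.** Secondary objective 6 (section 7A) is worded: "Evaluate to the tolerance to the ingestion of blue agave fructans Weber Tequilana through the use of breath test". Secondary objective 1 compares efficacy and tolerability at 5 g and 10 g but names no measure of tolerability.

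The theoretical framework, under tolerance and clinical adaptation to fructans, gives the only definition: "The tolerance Refers to the absence of gastrointestinal symptoms After their intake". It refers to low-digestible carbohydrates, the class to which fructans belong.

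The breath test subsection of section 8 says that the purpose is to "measure hydrogen and methane Concentrations previousle Exhaled In Patients randomized in visits 1 and 5". The visit descriptions in section 8 also place a test at Visit 3, before the randomisation step. On either schedule, the only test during treatment is at Visit 5.

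Symptom information is collected elsewhere:
- Patients keep an adverse-effect sheet, and there is medical questioning at Visits 4 and 5 (section 8).
- Side effects and rescue therapies, including simethicone and antispasmodics, are recorded (section 12).
- Losses are reported by arm with the reason for leaving (section 9).

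The main outcome and secondary variables I to V in section 10 contain no tolerance, symptom or breath-test variable, and the statistical analysis plan adds none.

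**The concern.** The measure named in the objective does not match the concept it is meant to evaluate. Of agave fructans, the framework says that their chemical bond "causes them to arrive intact to the intestine and can be subject to fermentation by the colon microbiota". Gas is therefore the expected consequence of taking the product, whether or not the patient has symptoms. A rise in hydrogen would confirm fermentation. It would not separate a patient who is comfortable from one who is not.

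Two errors of interpretation are possible. A rise in gas could be reported as poor tolerance, or a flat result as good tolerance, and the protocol supports neither step. The problem definition in section 5 says that tolerability limits long-term use of these fibre products, so readers will look for this conclusion.

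**Working it through.** **1. Concept against measure**

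| Item | Content | Where |
|---|---|---|
| Question | Tolerance to the fructans | Section 7A, secondary 6 |
| Definition of tolerance | No gastrointestinal symptoms after intake | Theoretical framework, tolerance subsection |
| Quantity measured | Exhaled hydrogen and methane | Section 8, breath test |
| What that quantity reflects | Bacterial fermentation of unabsorbed carbohydrate | Theoretical framework, breath test |
| Rule linking the two | None given | Sections 8 and 10, analysis plan |

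Of secondary variables I to V (stool form, stool frequency, butyrate, microbiota, glucose with HbA1c), none concerns breath gas or gastrointestinal symptoms. The missing rule is therefore not supplied later in the plan.

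**2. Who has an on-treatment reading**

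- Visit 4 is one month (± 5 days) after the start, and Visit 5 is a month after that: 1 + 1 = 2 months. This reproduces the two-month duration given in section 10 with the HbA1c variable.
- The tests at Visit 1 and, if done, Visit 3 come before treatment. On-treatment tests: one, at about two months.
- A patient who stops before Visit 5 has no on-treatment reading. If the reason was gastrointestinal symptoms, that is exactly the patient whom a tolerance question should count.

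**3. Precision of a symptom-based comparison**

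The planned size is 15 per arm (section 8). The event counts below are assumptions for illustration, since the documents give no expected symptom rates for these arms. The method is the Newcombe 95% interval for a difference in proportions, built from Wilson limits (l, u):

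- lower = d − √[(p1 − l1)² + (u2 − p2)²]
- upper = d + √[(u1 − p1)² + (p2 − l2)²]

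For 6/15 versus 3/15:
- p1 = 0.400, Wilson limits 0.198 to 0.643
- p2 = 0.200, Wilson limits 0.070 to 0.452
- d = 0.200
- lower = 0.200 − √(0.202² + 0.252²) = −0.12
- upper = 0.200 + √(0.243² + 0.130²) = 0.47

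| Assumed counts | Difference | 95% interval |
|---|---|---|
| 3/15 v 3/15 | 0 | −28 to +28 points |
| 6/15 v 3/15 | +20 points | −12 to +47 points |
| 9/15 v 3/15 | +40 points | +5 to +64 points |

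Only a very large dose difference would stand out.

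**The case against.** **Objective 6 may be a separate physiological question.** The framework lists assessment of intolerance to carbohydrate absorption among the uses of breath testing and says that fermentation causes symptoms. The symptom definition is one background sentence in a rough translation, not an endpoint definition. This gives a reason for doing the test, and the test should stay. It does not give a way to read tolerance from gas, and no other definition of tolerance replaces the one in the background.

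**A reader might infer that the symptom data serve no objective.** The documents do not support that. Secondary objective 1 is explicitly about tolerability, and the adverse-effect sheet fits it naturally. What is missing is the sentence that says so.

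**A reader might infer that the cited 2014 agave study shows gas and tolerance disagreeing**, since hydrogen rose with a "statistically significant difference in the groups That Took Agave inulin (5 and 7.5g) vs controls" and yet "the presence of symptoms was well tolerated by the healthy subjects". It does not. Bloating and flatulence rose at the same doses, so gas and symptoms moved together. They seem to conflict only if tolerance is taken to mean that mild symptoms are acceptable, which is not the protocol's definition.

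**A reader might infer that the test is badly timed**, because section 12 expects flatulence and bloating to settle: "reports of studies using the fiber, have shown that this effect is transient lasting 2 weeks". That statement is about symptoms, not gas. The framework also describes bacterial adaptation with regular intake, so comparing baseline with two months is a reasonable design for fermentation. The part that stands is narrower: patients who stop early have no on-treatment reading.

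**Other objectives also lack a variable**, for example quality of life and transit. True, but those name a measure that fits their question. Objective 6 names one that does not. The objection does support a low severity.

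**Conclusion.** The point holds, at low severity. Objective 6 names a fermentation measure for a question that the protocol itself defines by symptoms, and nothing in the plan converts one into the other. As written, the answer to objective 6 could not show whether patients tolerated the product, and it would leave out anyone who stopped before Visit 5. One secondary objective is affected, and the primary outcome is not.

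The conclusion assumes that the background definition is the intended meaning of tolerance, as it is the only one given. It also assumes that no annex contains a rule for interpreting gas values. The annexes are not in the supplied text, so the content and dating of the adverse-effect sheet could not be checked. The documents give no hydrogen or methane values, so no size can be put on a gas difference.

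**What to change.** 1. Reword secondary objective 6 so that the breath test evaluates fermentation, as the change in hydrogen and methane from baseline to Visit 5. Name which pre-treatment test is the baseline, and state that the result is not used to conclude tolerance.
2. State that tolerability under secondary objective 1 is judged in all patients who took at least one dose, from:
   - gastrointestinal symptoms on the adverse-effect sheet and at the Visit 4 and 5 questioning, shown by week if the sheet dates them;
   - use of simethicone or an antispasmodic;
   - stopping because of gastrointestinal symptoms.
3. Tabulate these for all four arms. Give 10 g versus 5 g alone as a descriptive difference in proportions with a 95% interval. Breath results may be shown beside the symptoms.

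The cost is one reworded objective, one added secondary variable and one table, with no new visit or procedure. If the sheet does not date symptoms, a week column is needed for the weekly display. The drawback is width: at 15 per arm the table describes tolerability and will not settle a modest dose difference.
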